## **2.0 OBJECTIVES**

### **2.1 Primary objectives**

To determine the recommended phase II dose of post-operative prophylactic NAC irradiation after nipple areola-sparing mastectomy and immediate reconstruction in patients with ductal carcinoma in-situ or invasive breast cancer.

### **2.2. Secondary objectives**

To provide extensive descriptive data regarding NAC-sparing surgery with reconstruction, including both surgeon experience and patient evaluation of cosmetic results. Survival and recurrence will be also assessed.

## **3.0 PATIENT SELECTION**

### **3.1 Inclusion Criteria**

- 3.1.1** Patients must have histologically confirmed in-situ or invasive breast carcinoma.
- 3.1.2** Tis, T1, T2 invasive or non-invasive carcinoma of the breast; lesion less than 4 cm.
- 3.1.3** Unifocal, multifocal or multicentric breast cancers that can be removed by nipple sparing mastectomy with negative surgical margins.
- 3.1.4** No extensive intraductal component or patient with distant metastases.
- 3.1.5** Patients must be > 18 years of age.

- 3.1.6** No concomitant or history of nipple discharge or skin involvement.
- 3.1.7** No prior history of malignancy (less than 5 years prior to study entry), except non-melanomatous skin cancer.
- 3.1.8** No prior history of radiation to the chest.
- 3.1.9** No collagenous disease (systemic lupus erythematosis, scleroderma, dermatomyositis). No previous non-hormonal therapy including radiation or chemotherapy for current breast cancer.
- 3.1.10** No patients with Paget's disease of the nipple.
- 3.1.11** No patients with co-existing medical conditions with life expectancy < 2 years.
- 3.1.12** No pregnant or lactating women.
- 3.1.13** ECOG 0 - 2.
- 3.1.14** Signed study-specific informed consent form prior to the study entry.

### **3.2 Exclusion Criteria (08-06-2013)**

- 3.2.1** Retroareolar breast cancer lesions within one cm. depth from the skin surface.
- 3.2.2** Concomitant or history of nipple discharge or skin involvement.
- 3.2.3** Patient with distant metastases.
- 3.2.4** Patient with extensive intraductal carcinoma.
- 3.2.5** Any previously irradiated ipsilateral breast cancer.
- 3.2.6** Patients with Paget's disease of the nipple.
- 3.2.7** Patients with collagenous diseases, as systemic lupus erythematosis, scleroderma or dermatomyositis.
- 3.2.8** Other malignancy, except non-melanomatous skin cancer, less than 5 years prior to participation in this study.
- 3.2.9** Patients who are pregnant or lactating due to potential exposure of the fetus to RT and unknown effects of RT to lactating females.
- 3.2.10** Positive surgical margins following nipple sparing mastectomy

### **3.3 Enrollment Procedures (07-03-2012)**

To enter a patient, the investigator or study team will contact the CRS representative. All eligibility requirements must be reviewed prior to the patient entering the study. The following information must be provided to the CRS representative:

- 1) Completed and signed protocol-specific eligibility checklist;
- 2) All pages of the original signed informed consent forms (ICFs), including HIPAA Form B.
- 3) Relevant source documents such as: subject medical history and physical exam, admission or discharge notes, diagnostic

reports, pathologic confirmation of diagnosis, and relevant subject-specific written communication.

### 3.3.1 Cancellation Guidelines

If a patient does not receive protocol therapy, the patient may withdraw. Contact the CRS representative, or e-mail the information including the reasons for withdrawal within 10 working days.

### 3.3.2 Emergency Registration

If an emergency registration takes place after business hours, the items listed in section 3.3 above must be submitted by the next business day.

## 4.0 TREATMENT PLAN

Week 1	NAC-sparing mastectomy with immediate reconstruction
Between weeks 5 to 8	Prophylactic NAC irradiation twice daily, minimum of 4 hours apart, for 5 days , preferable in consecutive working days;
2 weeks after irradiation	Chemotherapy, if indicated, at the discretion of the treating physician

## 4.1 Surgery

**4.1.1 NAC-sparing mastectomy:** Subcutaneous Mastectomy (SCM) to be performed, preserving the nipple and areola complex, after a frozen section of the tissue underneath the nipple-areola complex is sampled and found to be negative for tumor.

**4.1.2 Axillary Dissection or Sentinel Node Biopsy (SNB)** will be performed at surgeon's discretion.

**4.1.3 Reconstruction: Immediate reconstruction of the breast** will be performed by the plastic surgeon's discretion and patient's desire.

## 4.2 Radiation Therapy

### 4.2.1 Dose levels and schedule

Dose levels †	Description
Dose Level I = 20 Gy	10 fractions of 2.0 Gy
Dose Level II = 25 Gy (starting dose)	10 fractions of 2.5 Gy
Dose Level III = 30 Gy	10 fractions of 3 Gy
Dose Level IV = 35 Gy	10 fractions of 3.5 Gy

† Treatment will be delivered twice a day, minimum of 4 hours apart, **for 5 days**, preferable in consecutive working days.

**4.2.2 Treatment Planning and Imaging:** Treatment planning and delivery should be performed with the patient in supine position, on a breast board. A treatment planning CT scan will be required to define the clinical target volume (CTV) which will include the nipple-areola complex. At the time of CT Simulation, the NAC will be marked on the skin, to be seen on the CT images for planning. A second simple simulation might be performed to verify treatment parameters and treatment field on the patient, according to plan.

**4.2.3 Beam Angles/Treatment Position:** The patient will be treated in supine position, with electrons. The energy of the electrons assigned for treatment will be dependent on the plan to cover the area of NAC appropriately, as per radiation oncologist's discretion.

**4.2.4 External Beam Equipment:** Megavoltage equipment is required with a range of electrons energy.

### 4.2.5 Dose escalation/de-escalation design

The following are the four possible dose levels to be tested in the study:

Dose level I: 20 Gy total (2.0 Gy for 10 fractions)

**Dose level II: 25 Gy total (2.5 Gy for 10 fractions) (Starting Dose)**

Dose level III: 30 Gy total (3.0 Gy for 10 fractions)

Dose level IV: 35 Gy total (3.5 Gy for 10 fractions)

The patients will be receiving postoperative NAC irradiation using electrons **starting at Dose level II**. Dose levels will be escalated by 0.5 Gy per fraction for an overall 5 Gy increase per level up to 3.5 Gy per fraction and a total dose of 35 Gy. **Evaluable patients** will be defined as any eligible patient that begins NAC irradiation treatment.

DLT (dose-limiting toxicity), as defined in section 4.2.6, will be evaluated during radiation treatment period plus an **additional observation period of 30 days** following completion of NAC radiation.

We propose a **modification of standard dose-escalation design, treating cohorts of 2 to 6 patients per dose level of NAC irradiation**. The main features of the proposed escalation design is that (1) no more than 2 patients will experience DLT at a given radiation dose and (2) escalation to a higher dose occurs only after a cohort of 6 patients have been evaluated at a given radiation dose.

Dose escalation/de-escalation rules	
Number of patients with DLT at a given dose level	Escalation Decision Rule
0 or 1 out of 6 patients	Enter 6 patients at the next higher dose level.
2 out of 2 to 6 patients	Dose escalation stops. However, if the dose tested is dose level II, the starting dose level, then de-escalation occurs. In this case, dose level I will be tested in 2 to 6 patients.
The highest dose tested at which $\leq 1$ out of 6 patients experiences DLT will be declared the MTD and it will be the recommended phase II dose .	

Thus, as stated in the dose escalation/de-escalation rules above, if 0 or 1 patient experiences DLT (as defined in section 4.2.6) among 6 patients, the dose level will be judged to be acceptable. If this occurs, then a new cohort of 2 to 6 patients will be accrued at the next higher dose level. If 2 patients experience DLT among 2 to 6 patients at a given dose level, then the corresponding dose will be declared to be unacceptable. If the **starting dose level** (dose level II) proves to be unacceptable, then de-escalation occurs to dose level I and 2 to 6 patients will be enrolled at dose level I.

The **maximum tolerated dose (MTD)**, among the doses tested, will be determined as the highest **NAC irradiation** dose level at which  $\leq 1$  out of 6 patients experiences DLT. The MTD will be declared the **“potential” recommended phase II dose (RP2D)** of post-operative prophylactic NAC irradiation after NAC-sparing mastectomy **with reconstruction** in patients with ductal carcinoma in-situ or invasive breast cancer.

**Simultaneous enrollment:** Simultaneous enrollment will be permitted under the following circumstance:

- If  $j$  ( $j \leq 4$ ) patients have been treated at a given dose and there are no DLTs, patients  $(j+1)$  and  $(j+2)$  may be enrolled simultaneously at the same dose level.

For instance, the first two patients could be enrolled simultaneously, that is, patient 2 could be enrolled within <30 days apart after patient 1 has completed the radiation treatment. As another example, If the first patient to receive a NAC radiation dose level does not experience DLT, within the DLT evaluation period of minimum 35 days, patients 2 and 3 may be enrolled simultaneously at the same dose level; that is, patient 3 can be enrolled before patient 2 has been fully evaluated for DLT within <30 days apart after patient 2 has completed the radiation treatment.

#### **4.2.6 Definition of dose limiting toxicity (DLT)**

Dose limiting toxicity (DLT) is defined as any of the following toxicities occurring during radiation treatment period plus an **additional observation period of 30 days** following completion of NAC radiation:

- a) Grade 4 skin rash
- b) Grade 4 pain
- c) NAC necrosis
- d) Any toxicity requiring interruption of the NAC irradiation by > 2 weeks (14 calendar days), except if interruption is secondary to LINAC machine or unpredictable weather problems or unrelated medical conditions that would prevent the subject to come for treatment.
- e) Any grade 4 or 5 treatment-related toxicity

#### **4.2.7 Expansion cohort**

An additional expansion cohort of 12 patients will be enrolled at the “**potential**” recommended phase II dose (RP2D) **to confirm its safety**.

If safety is confirmed in the total 18 patients (6 from dose-finding part of study plus 12 from the expansion cohort) treated at the “**potential**” (RP2D, the corresponding dose will be declared the **RP2D**).

### **4.3 Chemotherapy**

**4.3.1** Chemotherapy, if indicated by oncologist, will be delivered at least 2 weeks from the last radiation treatment.

**4.3.2** The type of chemotherapy will be at discretion of the oncologist physician.

## **5.0 Clinical and Laboratory Evaluations**

### **5.1 Preoperative assessment:**

Preoperative assessment includes general medical status and organ function as well as tissue diagnosis and a work up for metastatic disease if applicable. The assessment will include standard history and physical examination, histology, laboratory and radiological tests as deemed appropriate by the operating surgeon.

### **5.2 Intraoperative parameters**

Intraoperative events and findings will be reported as routinely done in the operative report. Pathologic examination of the frozen section of the tissue underneath the NAC will be performed at the time of surgical procedure and results will be recorded in the study records. If pathology is positive, the patient will be taken off the study as screen failure.

### **5.3 Perioperative parameters**

The surgical team will monitor for complications in the usual manner and any complication will be treated accordingly. Duration of hospital stay, complications will be recorded.

### **5.4 Pathologic evaluation of specimens**

Pathologic examination of the frozen section of the tissue underneath the NAC will be performed at the time of surgical procedure and results will be recorded in the study records. If pathology is positive, the patient will be taken off the study as screen failure. If pathology is negative, the surgeon will then perform a Skin Sparing Mastectomy, sparing the NAC. If the patient's NAC tissue biopsy is negative by frozen, but positive after standard hematoxylin and eosin, the patient will be taken off the study and the discussion will be done with the patient about options of removal of the NAC or postoperative irradiation of NAC outside the protocol.

### **5.5 Photographs (07-15-2011)**

**5.5.1** Photographs shall be taken at the discretion of the P.I. and Sub-P.I.

### **5.6 Patient enrollment data**

**5.6.1** Complete history and physical examination

**5.6.2** Mammographic reports

**5.6.3** Pathology reports

## 5.7 Patient treatment data

- 5.7.1** Operative reports from mastectomy and reconstruction.
- 5.7.2** Toxicity reports: skin reaction(s) to radiation therapy including erythema, desquamation, etc.; any acute or unusual severe side effects of surgical procedures or radiation treatment
- 5.7.3** Radiation treatment: prescribed and delivered doses
- 5.7.4** Copies of dosimetry calculations
- 5.7.5** At least one photograph of the treated breast prior to initiation of treatment

## 5.8 Patient follow-up

- 5.8.1** Vital status
- 5.8.2** Disease status, classified local, regional, or distant
- 5.8.3** Site(s) and date of first failure in each category above
- 5.8.4** Relationship of the recurrence to the irradiated volume
- 5.8.5** Cosmetic evaluation by patient and physicians
- 5.8.6** Effects of treatment
- 5.8.7** Follow-up physical examination
- 5.8.8** Photographs will be taken at the discretion of the P.I. and Sub-P.I.
- 5.8.9** AE and Concomitant Medication reporting from post-operative visit up to 30 days post radiation treatment.

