#### **6.3.1 Specific risks of Prophylactic NAC Irradiation after NAC-sparing Mastectomy and Reconstruction.**

The addition of Prophylactic NAC irradiation after NAC-sparing Mastectomy and Reconstruction include necrosis of NAC, with a need for additional surgical procedure for repair; delayed wound healing, poor cosmesis secondary to permanent hypopigmentation or hyperpigmentation of the skin of the NAC or skin fibrosis.

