## **10.3 Interim Monitoring**

### **10.3.1 Role of the Research Team and the DSMC**

The Research Team will continuously monitor study accruals and adverse events from both surgery and radiation treatment. In particular, for the purpose of escalation and de-escalation (section 4.2) patients will be monitored closely during the 30 days after completion of NAC radiation treatment, and subsequently for any toxicity or adverse reaction to treatment. All toxicities, regardless their grade, will be recorded in the patient case report form using NCI/CTEP Common Terminology Criteria for Adverse Events (CTCAE) version 3.0.

The Sylvester Comprehensive Cancer Center's Data and Safety Monitoring Committee (DSMC) will monitor this protocol according to the Cancer Center's DSM Plan. In its oversight capacity, the DSMC bears responsibility for suspending or terminating this study.

DSMC oversight of the conduct of this trial includes ongoing review of accrual and adverse event data. The guidelines appearing in Sections 10.3.2, and 10.3.3 are offered for DSMC consideration in assessing accrual, adverse events. In addition, the DSMC will review reports from all audits, site visits, or study reviews pertaining to this clinical trial and take appropriate action.

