#### **Expansion cohort:**

An additional expansion cohort of 12 patients will be enrolled at the "potential" recommended phase II dose (RP2D).

If a radiation-related (possible, probable, or definite) death (grade 5 toxicity) occurs, enrollment will be suspended and continuation of the study will be reassessed by the DSMC.

Unacceptable radiation-related toxicity (possible, probable, or definite) is defined as grade 3, 4, or 5 adverse events, excluding grade 3 adverse events that resolve or down grade to grade 2 within 14 days.

Unacceptable radiation-related toxicity (possible, probable, or definite) is expected

to occur in no more than 10% of patients. If there is evidence that the true rate of this toxicity exceeds 20%, then the study should be suspended or possibly terminated early. Specifically, we suggest as a guideline for early termination a posterior probability of 90% or higher that the true rate exceeds 20%. The table below shows specific instances where this guideline is met, suggesting early termination, and due to evidence of excessive toxicity.

Number (%) of patients experiencing unacceptable radiation-related toxicity #	Total patients evaluated
3	3 to 5
4	6 to 9
5	10 to 12

#:Radiation-related toxicity (possible, probable, or definite) is defined as grade 3 or higher adverse events, excluding grade 3 adverse events that resolve or down grade to grade 2 within 14 days.

To illustrate the stopping guidelines, suppose that 5 evaluable patients in the expansion cohort have been assessed for radiation-related toxicity and 3 of them have experienced grade 4 unacceptable toxicity. (See row 1 of the above table.) Under this circumstance, the observed rate of unacceptable toxicity is 60%, resulting in a posterior probability of 92.7% (not shown) that the true underlying rate exceeds 20%, thereby suggesting early termination.

Posterior probabilities for the above table are calculated under a weak prior beta distribution with parameters  $\beta_1 = 0.2$  and  $\beta_2 = 1.8$ , which corresponds to an expected unacceptable radiation-related toxicity rate of 20% based on very limited information, roughly equal to having studied 2 patients. This prior distribution implies also a priori chance of only 18% that true rate is 20% or greater.

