## APPENDIX I (02-21-2013)

STUDY PARAMETER TABLE (See Section 5.0 for details)										
	SURGERY			PRIOR to RT	DURING RT	FOLLOW-UP AFTER TREATMENT			Long-term Follow-up	
Assessment	Pre-Op	Intra-Op	Post-Op	PRIOR to RT		From END of RT			From End of RT	
		Week 1-4		Week 1-7	Week 5-8	1 Mo ± 1 wk.	3 Mo ± 2 wks	6 Mo ± 2 wks	12 Mo ± 2 wks	Thereafter, Every 6 Mo (± 1 Mo) and in years 2-5 at the discretion of the Investigator
Informed Consent	X									
Biopsy	X									
Surgical Frozen Section Path		X								
Pathology	X		X							
History/Physical	X		X	X	X	X	X	X	X	
ECOG 0-2	X			X		X	X	X	X	
Mammogram	X									
Pregnancy test	X									
Labs per MD discretion	X									
Radiological tests per MD discretion	X	X								
Operative Report			X							
Photographs *				X		X	X	X	X	
NAC sparing mastectomy		X								
RT Treatment Plan					X					
Cosmesis				X		X	X	X	X	
AE Evaluation			X	X	X	X				

\* Photographs will be taken at the discretion of the PI and Sub-PI

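### Scheduled adverse-event collection stops about 30 days after radiation while section 10.3.1 continues toxicity monitoring, and no window is set for counting later NAC toxicity in the expansion guideline or the RP2D confirmation

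*Combined protocol and SAP*

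**What the plan says.** - **Collection.** Section 5.8.9 lists "AE and Concomitant Medication reporting from post-operative visit up to 30 days post radiation treatment" among the follow-up items. In the Appendix I calendar, the row "AE Evaluation" is marked post-op, before radiation, during radiation and at 1 month. It is blank at 3, 6 and 12 months, although history/physical and cosmesis are marked at those visits.
- **Monitoring.** Section 10.3.1 states that "patients will be monitored closely during the 30 days after completion of NAC radiation treatment, and subsequently for any toxicity or adverse reaction to treatment". It adds that "All toxicities, regardless their grade, will be recorded in the patient case report form", graded by CTCAE version 3.0. Neither sentence has an end date.
- **Risks.** For prophylactic NAC irradiation, section 6.3.1 names NAC necrosis that may need further surgery, and "delayed wound healing, poor cosmesis secondary to permanent hypopigmentation or hyperpigmentation of the skin of the NAC or skin fibrosis".
- **Use of the data.** Dose-limiting toxicity covers the radiation period plus an "additional observation period of 30 days" (4.2.6). The toxicity table (10.2), the expansion guideline (10.3.2) and the confirmation of the recommended phase II dose (RP2D) in 18 patients (4.2.7) give no time window.

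**The concern.** The primary objective is the RP2D, and the expansion cohort exists to confirm that the dose is safe. The protocol itself expects late effects. Section 1.3 calculates a biologically effective dose for late effects at the top dose level, and section 6.3.1 lists fibrosis and permanent pigment change. Permanence cannot be judged by day 30, and necrosis or delayed healing may also first appear after it.

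The calendar and 5.8.9 tell a site to stop adverse-event reporting at about day 30, and 10.3.1 tells it to carry on. Section 7.2 says adverse events are reported at scheduled times, and none is scheduled after month 1. A site that follows the calendar would supply acute toxicity almost exclusively. Because the downstream rules name no window, nothing in the plan would show that later toxicity is missing, or that it was counted for some patients and not for others.

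**Working it through.** **1. The passages compared**

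| Place | Collection after day 30? | CTCAE grade and attribution? |
|---|---|---|
| 5.8.9 | No | Not applicable |
| Appendix I, adverse-event row | No (last mark at 1 month) | Not applicable |
| 10.3.1 | Yes, no end date | Grade yes; no visit or form given |
| 5.8.6, effects of treatment | Yes | None stated |
| 5.10, cosmesis to 12 months | Yes | Neither; feeds no safety rule |
| 7.3, serious events | No general end date | Serious events only |
| 10.2, 10.3.2, 4.2.7 | No window stated | Depends on what is collected |

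The Appendix I columns were read from an extracted table, so their alignment is inferred. It agrees with 5.8.9.

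**2. The plan's own figure.** Section 10.3.2 uses a Beta(0.2, 1.8) prior and stops when P(rate > 20%) is at least 90%. For 3 events in 5 patients the posterior is Beta(0.2 + 3, 1.8 + 2) = Beta(3.2, 3.8), and P(rate > 0.20) = 0.9275, against the stated 92.7%. The upper ends of the table rows also agree: 4/9 gives 0.904 and 5/12 gives 0.920. The guideline's arithmetic is therefore sound. The open question is which events enter the count.

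**3. Coverage.** Appendix I has four visits in the first year after radiation (1, 3, 6 and 12 months). One has adverse-event evaluation and 3 of 4 do not, which leaves about 11 of 12 months without scheduled evaluation.

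**4. How likely is a late event?** The documents give no late rate, so r is an assumption. With 18 patients at the RP2D (6 + 12), the expected number is 18r and P(at least one) = 1 − (1 − r)^18.

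| Assumed r (late grade 3+) | Expected events | P(at least one) |
|---|---|---|
| 5% | 0.9 | 0.603 |
| 10% | 1.8 | 0.850 |
| 20% | 3.6 | 0.982 |

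**5. Could the window change the expansion guideline?** I applied the table in 10.3.2 sequentially to 12 patients, stopping at 3 or more events for n = 3–5, 4 or more for n = 6–9, and 5 or more for n = 10–12. The early rate e counts patients with an event by day 30. The late rate l counts patients whose only qualifying event comes later, so the total is e + l.

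| Assumed e | Assumed l | P(guideline met), events to day 30 only | P(guideline met), late events also counted |
|---|---|---|---|
| 5% | 15% | 0.2% | 12.5% |
| 10% | 10% | 1.5% | 12.5% |
| 10% | 20% | 1.5% | 36.0% |

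The last column is an upper bound, because it treats each late event as known before the next patient is assessed.

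**6. The 14-day exclusion.** The guideline counts grade 3–5 events, "excluding grade 3 adverse events that resolve or down grade to grade 2 within 14 days". A grade 3 event starting on day d needs observation to day d + 14, and d + 14 > 30 when d > 16. For onset on days 17–30, the 14-day status falls after reporting closes under 5.8.9.

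**The case against.** A reader might infer that late NAC effects are shut out of the toxicity tables, the expansion guideline and the RP2D decision. The documents do not support that. Section 10.3.1 requires later monitoring and recording of all toxicities, and 5.8.6 collects effects of treatment in follow-up. Sections 7.3.1 and 7.3.2 require serious events to be reported with no general 30-day limit. Sections 10.2, 10.3.2 and 4.2.7 exclude nothing by date. Necrosis needing reoperation could well qualify as serious and reach the safety committee (DSMC). This stands: late events are unscheduled and their role is undefined, but they are not barred.

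A reader might also infer that the 14-day exclusion cannot be operated for events starting after day 16. That does not follow either. A grade 3 event counts unless it is shown to have improved, so one with unknown status counts, which is conservative. Section 11.4 also asks for source documentation of resolution, and the 1-month visit has a ±1 week margin. What remains is only that following open events is not explicitly required.

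Nor are all the named risks late. NAC necrosis is a dose-limiting toxicity inside the window, and delayed healing can show before day 30. Fibrosis and permanent pigment change are the clearest late examples. Cosmesis to 12 months captures part of them, and the documents do not show that they would reach grade 3.

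The answer to these objections is only partial. Serious-event reporting need not capture a non-hospitalised grade 3 wound or fibrosis event. Neither 5.8.6 nor cosmesis carries a CTCAE grade or attribution.

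**Conclusion.** The point holds as an inconsistency with a gap behind it. Sections 5.8.9 and Appendix I conflict with 10.3.1 on toxicity collection after day 30. No graded, attributed collection is scheduled after month 1, and the expansion guideline and RP2D confirmation do not say which period they cover. A site following 5.8.9 and Appendix I would confirm the RP2D essentially on acute toxicity, with only partial cover from serious-event reporting, 5.8.6 and cosmesis.

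The firm measure of size is 3 of 4 first-year visits without adverse-event evaluation. The 60% to 98% chance of at least one late event in 18 patients, and the shift from 1.5% to at most 36.0% in the guideline, rest on assumed rates. They show that the window can matter, not that it will.

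**What to change.** 1. Reconcile 5.8.9 and Appendix I with 10.3.1. Keep full reporting to day 30. Then record at least radiation-related (possible, probable or definite) skin, NAC, wound and reconstruction toxicities by CTCAE grade at the existing 3-, 6- and 12-month visits. Align the wording of 10.3.1 on all toxicities with the scope chosen, so that no conflict remains.
2. Require grade 3 or higher events open at day 30 to be followed until their 14-day status is known.
3. In 10.2, tabulate toxicity by dose separately for up to 30 days and after 30 days, and report the later events to the DSMC.
4. In 10.3.2 and 4.2.7, state the window used for the expansion guideline and for the RP2D confirmation, and when a patient counts as evaluated. If the window runs past day 30, confirm that the 10% and 20% reference rates still apply, and say whether confirmation waits for the last patient's later visits. If it stays at 30 days, say that the RP2D is confirmed on acute toxicity.

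The cost is protocol and form wording, plus a short adverse-event page at three visits that already include a physical examination. The reported toxicity rate may be less favourable. Attribution will be harder in patients on chemotherapy, which section 4.3 allows from 2 weeks after radiation. A window longer than 30 days would also delay confirmation of the RP2D. No visit or treatment is added.
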